#### 5. Trial Design

The principal research objective is to assess the safety and efficacy of the Imperial Microprobe array biosensor for continuous monitoring of ISF glucose. The study will be conducted over four phases:

##### **Phase 1:**

**Purpose:** to assess safety of the device and to demonstrate proof of concept over a period of six hours in 16 non-diabetic volunteers.

##### **Primary outcome:**

- Skin inflammation

##### **Secondary outcomes:**

- Skin Penetration
- Pain score
- Detectable signal
- Correlation with venous blood glucose
- Clarke error grid
- Magnitude of current

Non-diabetic subjects will be recruited for phases 1 and 2 by poster advertisement placed at Imperial College Healthcare NHS Trust and Imperial College campuses.

***Subject inclusion criteria*** Subjects may be recruited if:

- Adults over 18 years of age

***Subject exclusion criteria*** Subjects are excluded if:

- History of upper limb neuropathy or radiculopathy
- History of pre-existing skin condition
- Pregnant or planning pregnancy in next 12 months
- Breastfeeding
- Enrolled in other clinical trials
- uncontrolled concurrent illness

- Have active malignancy or under investigation for malignancy

**Subject withdrawal criteria** Subjects will be withdrawn from the study in the case of:

1. Loss of capacity to give informed consent
2. Development of skin disease or upper limb neuropathy or radiculopathy
3. Terminal illness

Withdrawal will be immediate.

Participant information sheets will be given to potential subjects and, after a minimum of 48 hours and following any questions, informed consent will be taken.

Subjects will be asked not to apply any cosmetic formulations on the non-dominant forearm for 7 days prior to the study.

**Visit:**

- Attend the Wellcome Trust-Sir John McMichael Clinical Research Facility at the Hammersmith Hospital campus of Imperial College between 9:00 - 10:00 am. Female subjects of childbearing age will have a urine pregnancy test performed.
- The outer margin of a 2 cm^2 skin area on the ventral aspect of the non-dominant forearm will be marked before the application of sterile microprobe array to the center of this skin area. The marked skin area will be shaved if hairy. Microprobe insertion will be achieved by applying gentle pressure. Microprobe array will be secured in place with an adhesive plaster for six hours with 5 minutes sampling as moving average of 1 minute intervals.
- An 18-G intravenous cannula will be inserted in the non-dominant upper limb for venous sampling. Throughout the 6 hours, 2.5mL venous blood will be taken at 15 minutes interval and will be distributed for venous glucose estimation using YSI analyser. Maximum blood volume collected over study visit duration is 60mL.
- Six hours after microprobe insertion (at 16:00), the microprobe array and intravenous cannula will be removed.
- Skin area around the microprobe array will be inspected at 1, 2 hours post-insertion and after device removal by a doctor for any evidence of skin inflammation using a 4-point scale (none, mild, moderate and severe).
- Following removal of the device, the microprobe treated skin area will be examined using confocal microscopy imaging technique to confirm penetration and examine the created microchannels.
- Microprobe arrays will be examined for integrity before and after application using scanning electron microscopy (SEM).
- Visual analogue scale (VAS) will be used to assess pain resulting from microprobe insertion in comparison with pain resulting from blood sampling.

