## **Phase 2:**

**Purpose:** to assess safety of the device over 24 hours and efficacy over 6 hours in 16 non-diabetic volunteers.

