### **Visit:**

- Attend the Wellcome Trust-Sir John McMichael Clinical Research Facility at the Hammersmith Hospital campus of Imperial College between 9:00 - 10:00 am
- The outer margin of a 2 cm^2 skin area on the ventral aspect of the non -dominant forearm will be marked before the application of sterile microprobe array to the center of this skin area. The marked skin area will be shaved if hairy. Microprobe insertion will be achieved by applying gentle pressure. Microprobe array will be secured in place with an adhesive plaster for 24 hours with 5 minutes sampling as moving average of 1 minute intervals for the first six hours.
- An 18-G intravenous cannula will be inserted in the non-dominant upper limb for venous sampling. Throughout the 6 hours, 2.5mL venous blood will be taken at 15 minutes interval and will be distributed for venous glucose estimation using YSI analyser.
- Six hours after microprobe insertion (at 16:00), the intravenous cannula will be removed and the subject will be allowed home with the implanted microprobe array.
- Subject will attend the research unit between 09:00 - 10:00 the following day. 2.5mL venous blood will be taken for venous glucose estimation using YSI analyser before removal of the array after an implantation period of 24 hours. Maximum blood volume collected over study visit duration is 62.5mL.
- Skin area around the microprobe array will be inspected at 1, 2, 6 hours post insertion and after removal of the device by a doctor for any evidence of skin inflammation using a 4-point scale (none, mild, moderate and severe).
- Following removal of the device, the microprobe treated skin area will be examined using confocal microscopy imaging technique to confirm penetration and examine the created microchannels.
- Microprobe arrays will be examined for integrity before and after application using SEM.

- Visual analogue scale (VAS) will be used to assess pain resulting from microprobe insertion in comparison with pain resulting from blood sampling.

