## 7. Timescale

It is anticipated that the studies will take place over 4 years. Non-diabetic subjects will be recruited to the study for phase 1 and 2 (2 visits). Subject with type 1 diabetes will be recruited for phases 3 and 4 of the study for up to 12 - 18 months, with a total of 2 visits in that timeframe.

**8. Potential risks and benefits** The potential risks and burdens for research participants are as follows:

Skin inflammation may occur with the use of microprobe arrays. A literature review shows this to be minimal and transient. Subjects will be examined regularly by a doctor to assess the degree of any inflammatory reaction and the need for any intervention (ending the study or the use of local/systemic therapy if required).

Pain may result from microprobe array insertion. A literature review shows this to be absent or very minimal when compared to traditional needles or lancets. The array will be inserted with gentle manual pressure and pain score will be assessed in phases 2, 3 and 4.

In all visits (excluding phase 4) there is either a venous blood test or insertion of an intravenous cannula. These have the potential to cause discomfort. This will be minimised by experienced research personnel performing the procedure and appropriate use of equipment and aseptic technique.

In phases 3 and 4, subjects will have a continuous glucose-monitoring sensor (iPro2, Medtronic) inserted in anterior abdominal wall subcutaneous tissue. Sensor insertion can be associated with some discomfort but the insertion devices are spring-loaded with introducers, making the process rapid and often painless. Any discomfort will be minimised by adhering to manufacturer's instructions.

Assessment of efficacy of the device will be in comparison to venous glucose levels and a commercially available continuous glucose sensor over a period of twenty-four hours as in-patients. 2.5 mL venous blood will be taken at 30 minutes intervals apart from the period between 11:00 - 22:00 when the blood will be taken hourly.

During studies involving subjects with type 1 diabetes, subjects will adhere to their usual practice of diabetes management.

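### Skin inflammation, the sole primary outcome of Phases 1 and 2, is scored only after insertion, so redness already present cannot be separated from a device effect

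*Protocol*

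**What the plan says.** In Section 5 of the Protocol, the primary outcome of Phase 1 and of Phase 2 is the same single item, "Skin inflammation". It is not defined further, either as an absolute score or as a change. Phase 1 runs "over a period of six hours in 16 non-diabetic volunteers"; the purpose of Phase 2 is "to assess safety of the device over 24 hours and efficacy over 6 hours in 16 non-diabetic volunteers".

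The assessment times are fixed in the visit descriptions. For Phase 1: "Skin area around the microprobe array will be inspected at 1, 2 hours post-insertion and after device removal by a doctor". For Phase 2: "Skin area around the microprobe array will be inspected at 1, 2, 6 hours post insertion and after removal of the device by a doctor". The doctor looks for any sign of inflammation and grades it none, mild, moderate or severe. No rule is given for attributing a grade to a cause.

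Before application the site is outlined on the forearm, and "The marked skin area will be shaved if hairy". The array is then pressed in. No skin score is scheduled between these steps.

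Section 10 states that the study has no control or comparison group and that its outcomes are absolute. A comparison skin site, the iPro2 site, appears only in Phases 3 and 4, where skin inflammation is a secondary outcome.

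**The concern.** In a single-arm study with no control site, the subject's own skin before insertion is the only available reference for a local reaction. The Protocol does not record it. It also introduces a possible cause of redness unrelated to the array, because hairy sites are shaved shortly before insertion and the first score follows at 1 hour.

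A mild grade at 1 or 2 hours in Phases 1 and 2 could then reflect the array, the shaving, or redness present on arrival, and nothing in the record would say which. What is at stake is the interpretation of the main safety result. The scores also have uses during the trial: Section 8 links the degree of inflammation to decisions on intervention, and Section 20 has the management team review data after each visit cycle before the study proceeds.

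**Working it through.** **No stated figure to reproduce.** The Protocol gives no inflammation rate, threshold, alpha or power. Section 10 justifies the sample size by comparability with other early studies and by feasibility. The check is therefore a reading of the schedules, followed by an illustration.

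**Step 1: skin scores scheduled in each phase (Section 5).**

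| Phase | Role of skin inflammation | Before insertion | After insertion | Comparison site |
|---|---|---|---|---|
| 1 | sole primary | none | 1 h, 2 h, removal (6 h) | none |
| 2 | sole primary | none | 1 h, 2 h, 6 h, removal (24 h) | none |
| 3 | secondary | none | 1 h, 2 h, 6 h, removal (24 h) | iPro2 site |
| 4 | secondary | none | removal (day 6) | iPro2 site |

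**Step 2: can anything else serve as a baseline?** Four safeguards bear on the skin:
- exclusion for a history of a skin condition (and of diabetic dermopathy in Phase 3);
- seven days without cosmetics on that forearm;
- withdrawal if skin disease develops;
- a routine clinical examination before insertion in Phase 3.

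Each lowers the chance of abnormal skin. None is a graded score of the marked area on the day, and the clinical examination is not listed for Phases 1 and 2. By contrast, the arrays themselves are examined by electron microscopy both before and after use.

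**Step 3: weight of one score.** With n = 16 per phase, 1/16 = 6.25 percentage points.

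**Step 4: illustration.** Let p be the probability that a subject shows redness not caused by the device that is graded at least mild. The documents do not give p, so the range is an assumption. Subjects are taken as independent.

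- Expected number of such scores: 16 × p.
- Chance of at least one: 1 − (1 − p)^16.
- Observed rate if the device itself causes inflammation in 10% (also assumed, and independent of background redness): 1 − (1 − p)(1 − 0.10).

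| p (assumed) | Expected among 16 | Chance of at least one | Observed rate when the device rate is 10% |
|---|---|---|---|
| 2% | 0.32 | 28% | 11.8% |
| 5% | 0.8 | 56% | 14.5% |
| 10% | 1.6 | 82% | 19% |
| 20% | 3.2 | 97% | 28% |

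For example, at p = 5%: 16 × 0.05 = 0.8; 1 − 0.95^16 = 0.56; 1 − 0.95 × 0.90 = 0.145.

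Because shaving is conditional, p averages over shaved and unshaved subjects, and redness counts only if it lasts to a scoring time. The lower rows may be nearer the truth; the documents cannot settle this.

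**The case against.** The strongest reply is that the Protocol nowhere tells anyone to count earlier redness as a device effect. It asks a doctor to grade what is seen, and the definition of the outcome may sit in an analysis plan that is not shown. This stands as far as it goes: the documents support saying that the causes cannot be separated, not that prior redness is counted against the device. It does not remove the gap, because an analysis plan can define change from baseline only if a baseline was scored.

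A second reply is that any error would overstate harm, which is the cautious direction for a safety outcome, and that no formal threshold depends on the rate. That is fair and limits the severity. The scores still inform reviews during the trial, and an inflated rate would misdescribe the device.

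A third is that the shaving argument fades with time. This also stands. It applies mainly to the 1- and 2-hour scores, less to the 24-hour scores, and is implausible for the day-6 score in Phase 4.

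Two stronger readings are tempting, and neither is supported:
- **Carry-over from a first array.** Section 7 says "Non-diabetic subjects will be recruited to the study for phase 1 and 2 (2 visits"), and both phases use the same forearm. This suggests, but does not state, that the same volunteers attend both. No text requires the same spot, and Section 20 places management reviews between visit cycles. Residual marks are a possibility, not a documented problem.
- **Bias against the array in Phases 3 and 4.** This would need the abdominal iPro2 site to be left unshaved. The Protocol is silent on how that site is prepared, so no bias can be inferred.

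**Conclusion.** The point holds for Phases 1 and 2. The sole primary outcome is an ungated post-insertion grade with no pre-insertion score, no comparison site and no attribution rule, so pre-existing or shaving-related redness is inseparable from a device reaction, above all at 1 and 2 hours. Each misattributed score shifts the phase result by 6.25 percentage points. How many such scores to expect is unknown: the range of 0.32 to 3.2 per 16 subjects rests wholly on an assumed background rate of 2% to 20%.

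In Phases 3 and 4 the missing baseline is worth closing for consistency, but no bias is shown there. This is a low-cost improvement to the assessment schedule and does not make the study unsound.

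**What to change.** In the Phase 1 and Phase 2 visit descriptions, add a score of the marked area on the same 4-point scale, taken after any shaving and immediately before insertion. For consistency, add the same step to the Phase 3 and Phase 4 visits, and score the iPro2 site before its sensor is inserted.

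State that skin inflammation will be reported as new or worsened relative to that score, alongside the absolute scores at each time.

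The change needs no rule making insertion depend on the pre-insertion grade, and no requirement that one particular doctor make every assessment. It will not separate the array from other causes that begin after insertion, such as the adhesive plaster.

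The cost is one further inspection and one form field per visit (two fields where the iPro2 site is scored as well). Sample size and number of visits do not change.

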## **Phase 2:**

**Purpose:** to assess safety of the device over 24 hours and efficacy over 6 hours in 16 non-diabetic volunteers.

### **Primary outcome:**

- Skin inflammation

### **Secondary outcomes:**

- Skin Penetration
- Pain score
- Correlation with venous blood glucose
- Clarke error grid

Same inclusion, exclusion and withdrawal criteria as phase 1

Subjects will be asked not to apply any cosmetic formulations on the non-dominant forearm for 7 days prior to the study.

Participant information sheets will be given to potential subjects and, after a minimum of 48 hours and following any questions, informed consent will be taken.

### **Visit:**

- Attend the Wellcome Trust-Sir John McMichael Clinical Research Facility at the Hammersmith Hospital campus of Imperial College between 9:00 - 10:00 am
- The outer margin of a 2 cm^2 skin area on the ventral aspect of the non -dominant forearm will be marked before the application of sterile microprobe array to the center of this skin area. The marked skin area will be shaved if hairy. Microprobe insertion will be achieved by applying gentle pressure. Microprobe array will be secured in place with an adhesive plaster for 24 hours with 5 minutes sampling as moving average of 1 minute intervals for the first six hours.
- An 18-G intravenous cannula will be inserted in the non-dominant upper limb for venous sampling. Throughout the 6 hours, 2.5mL venous blood will be taken at 15 minutes interval and will be distributed for venous glucose estimation using YSI analyser.
- Six hours after microprobe insertion (at 16:00), the intravenous cannula will be removed and the subject will be allowed home with the implanted microprobe array.
- Subject will attend the research unit between 09:00 - 10:00 the following day. 2.5mL venous blood will be taken for venous glucose estimation using YSI analyser before removal of the array after an implantation period of 24 hours. Maximum blood volume collected over study visit duration is 62.5mL.
- Skin area around the microprobe array will be inspected at 1, 2, 6 hours post insertion and after removal of the device by a doctor for any evidence of skin inflammation using a 4-point scale (none, mild, moderate and severe).
- Following removal of the device, the microprobe treated skin area will be examined using confocal microscopy imaging technique to confirm penetration and examine the created microchannels.
- Microprobe arrays will be examined for integrity before and after application using SEM.

- Visual analogue scale (VAS) will be used to assess pain resulting from microprobe insertion in comparison with pain resulting from blood sampling.

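### Does the next-day venous glucose draw in Phase 2 need a stated array reading to pair with?

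*Protocol*

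**What the plan says.** The Phase 2 Purpose (Protocol, Section 5) sets a 24-hour horizon for safety and a six-hour horizon for efficacy, in 16 non-diabetic volunteers. The primary outcome is skin inflammation. Two secondary outcomes use venous glucose: "Correlation with venous blood glucose" and the Clarke error grid.

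The Phase 2 Visit text keeps the array in place for 24 hours and specifies "5 minutes sampling as moving average of 1 minute intervals for the first six hours". On venous sampling it says "Throughout the 6 hours, 2.5mL venous blood will be taken at 15 minutes interval". Then "Six hours after microprobe insertion (at 16:00), the intravenous cannula will be removed", and the subject goes home wearing the array. At the return visit between 09:00 and 10:00 the next day, "2.5mL venous blood will be taken for venous glucose estimation using YSI analyser before removal of the array". The blood budget is given as "Maximum blood volume collected over study visit duration is 62.5mL". The pain scale sets "pain resulting from microprobe insertion in comparison with pain resulting from blood sampling".

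Phase 1 uses the same six-hour venous schedule without a second day, and there "Maximum blood volume collected over study visit duration is 60mL". Phase 3 also has a 24-hour wear, but its recording instruction carries no six-hour limit.

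**The concern.** Correlation and the Clarke error grid both need an array value and a venous value at the same time. The last array recording that Phase 2 specifies ends at 16:00 on day 1, and the extra venous sample comes the next morning. Nothing in the protocol says that recording continues, restarts or is spot-read at that visit. Followed to the letter, the sample would enter neither glucose outcome.

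Two things would be at stake. The first is burden: the cannula came out the day before, so the sample needs fresh venous access, and Section 8 counts venous blood tests among the burdens of taking part. The second is lost information: the array is removed at that visit, so a reading not taken then cannot be recovered, and these are the only Phase 2 samples that could show how the array reads near 24 hours.

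**Working it through.** **Inputs (Protocol, Section 5).** Draw volume 2.5 mL; six hours at 15-minute intervals; one next-day draw; stated maxima of 60 mL (Phase 1) and 62.5 mL (Phase 2); 16 subjects in Phase 2; 20 subjects with 40 venous samples each in Phase 3.

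**1. Is the next-day draw a planned one?** Draws in six hours = 6 × 60 / 15 = 24.
- Phase 1: 24 × 2.5 = 60 mL, the stated maximum.
- Phase 2: (24 + 1) × 2.5 = 62.5 mL, the stated maximum.
- Counting both ends of the six hours instead gives 25 draws on day 1. That is 25 × 2.5 = 62.5 mL in Phase 1 (stated 60) and 26 × 2.5 = 65 mL in Phase 2 (stated 62.5). Neither fits.

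So 24 + 1 is the count that fits both phases. The next-day draw is deliberate and is counted in the blood budget.

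**2. How far is it from the specified recording?** Insertion = 16:00 − 6 h = 10:00. Attendance at 09:00–10:00 the next day is 23–24 h after insertion and 17–18 h after 16:00. The protocol gives no clock time for the draw itself, so these ranges rest on the attendance window.

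**3. How much of the Phase 2 data is affected?**
- All draws: 16 × 25 = 400.
- Draws inside the recording window: 16 × 24 = 384.
- Draws with no stated array value: 16 × 1 = 16, and 16 / 400 = 4%.
- Specified array values per subject: 6 × 60 / 5 = 72, all in the six hours that hold the 24 day-1 draws.

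**4. Does any stated aim depend on the 16?**

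| Stated aim or outcome | Needs a pair at about 24 h? |
|---|---|
| Skin inflammation (primary) | No: graded by inspection |
| Skin penetration | No: confocal microscopy after removal |
| Pain score | No: uses no array glucose value |
| Efficacy over six hours (correlation, Clarke grid) | No: 384 draws fall in the recording window |
| Efficacy over 24 hours | Not a Phase 2 aim; Phase 3 plans 20 × 40 = 800 venous samples with recording over the wear |

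**5. Do any two statements conflict?** No. The six-hour recording limit agrees with the six-hour efficacy aim. The limit applies to the regular five-minute regime, and the text does not rule out a single reading at the return visit.

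**The case for a change.** The best case for a change is that this is a matter of data collection, not analysis. An analysis plan that is not shown here could settle how a pair is used, but it cannot supply a reading that nobody took. Phase 3 uses nearly the same recording instruction without the six-hour limit, so the Phase 2 limit looks intended, and staff following it have no instruction to record on day 2. A research blood test should have a stated use, and one clause would provide it.

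Part of this stands. The protocol does not give the purpose of the draw, and a clause would have been tidier. But the objection identifies an unstated detail, not a wrong or conflicting rule. The draw is placed before array removal, an order that has little point unless the array is to be read, so staff have a plain cue to take a spot reading. Nor is it certain that the draw is otherwise idle. Pain from blood sampling is a comparator for the pain score, and the text does not confine it to day 1, although the day-1 sampling already supplies that comparison.

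The possible remedies also pull in opposite directions. Adding a reading assumes that the recorder can be reconnected, and the protocol does not describe the recording hardware. Dropping the draw would discard the only pair near 24 hours if a reading was intended. The document does not show which was meant.

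**Conclusion.** No change follows. The observation is accurate: 16 of 400 planned Phase 2 draws (4%) have no stated array reading. It is a gap that staff and analysts can fill sensibly, and it alters no planned result.

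- If a spot reading is taken, up to 16 extra pairs exist, one per volunteer. They lie outside the six-hour efficacy aim and are naturally treated as descriptive.
- If none is taken, the cost is one 2.5 mL draw per volunteer, openly counted in the maximum volume. The 16 venous values go unpaired, and Section 10 already allows unused data to be set aside with justification.

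Either way, the primary outcome, the six-hour correlation and the six-hour Clarke grid rest on the same data as planned, and Phase 3 carries the 24-hour question.

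This rests on two assumptions: that the draw count is 24 + 1, which the stated volumes in both phases support, and that the Phase 2 efficacy analysis keeps to the six hours given in its Purpose.
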